1 SYNOPSIS

Clinical Investigation Title	Pediatric Performance and Satisfaction of Oticon Medical Ponto on Softband
Investigation Code	BC117
Investigational Device (s)	Oticon Medical Ponto sound processor on Ponto Softband solution
Principal investigator(s):	N/A – online survey, Oticon Medical, LLC
Sponsor:	Oticon Medical AB [name]
Objective(s):	Primary Objective 
• Evaluate subjectively hearing performance of Oticon Medical Ponto sound processors on Ponto Softband• Evaluate subjectively overall satisfaction of Oticon Medical Ponto sound processors on Ponto Softband
Methodology:	Observational survey study
Inclusion/exclusion criteria:	1. Consent provided 2. Parent or primary caregiver of child (< 18 years) currently using a Ponto Softband for Ponto Sound Processor
Endpoints	Primary Endpoints 
• Overall PEACH scores• Overall GCBI scores• Outcomes of satisfaction questionnaire
Duration of study period:	24 months or when targeted number of participants (40) have been enrolled.
Number of participants targeted:	40
Investigation plan prepared by:	[name], Clinical Project Manager, Oticon Medical, LLC [name], Clinical Research Manager, Oticon Medical, LLC

23 APPENDICES **12****3 LIST OF ABBREVIATIONS**

AOM	Age of Majority
BAHS	Bone Anchored Hearing System
CIP	Clinical Investigation Plan
EC	Ethics Committee
EDC	Electronic Data Capture
GCBI	Glasgow Children's Benefit Inventory
GDPR	General Data Protection Regulation
ICF	Informed Consent Form
IRB	Institutional Review Board
ISO	International Organization for Standardization
OM	Oticon Medical
PEACH	Parent's Evaluation of Aural/Oral Performance of Children
SIN	Subject Identification Number

4 INTRODUCTION

4.1 Background

There are two pathways by which physical sound waves can be transformed into mechanical vibrations that stimulate the cochlea in the inner ear: air conduction and bone conduction. In air conduction, an acoustic signal travels through the outer and middle ear and arrives at the cochlea. In bone conduction, an acoustic signal bypasses the outer/middle ear and vibrates the bones of the skull to stimulate the cochlea. Both air and bone conduction support the same conversion mechanism in the cochlea where mechanical vibrations are converted into neural impulses to produce the perception of hearing.

Thus, for patients who are unable to reliably transmit acoustic signals through air conduction, e.g., those with conductive hearing losses (CHL) or mixed hearing losses (MHL), hearing loss following a middle ear disease (e.g., chronic otitis media, cholesteatoma, otosclerosis or other ossicular diseases), or malformations such as aural atresia and/or microtia, bone conduction hearing systems can be used to bypass conductive impairment in the ear canal or middle ear, and stimulating the cochlea directly via skull bone vibrations. For single-sided deafness (SSD), one utilizes the vibrations that are transmitted in the same manner via the skull bone to the (functioning) cochlea on the contralateral side.

Bone Anchored Hearing Systems (BAHS) have been used since the late 1970s and can be divided into two types: 1) direct drive and 2) skin drive. Direct drive denotes systems where the vibrations are transmitted directly to the bone (e.g., through an abutment connected to an osseo-integrated implant), while in a skin drive solution there is a layer of soft tissue between the transducer and the bone (e.g., when utilizing a softband).

A softband solution, in this investigation, the Ponto Softband solution is suitable for children with conductive/mixed hearing loss and single-sided deafness. It can also be used by adults who don't benefit from conventional hearing aids, or those who have temporary ear problems such as blockages or infections. Worn around the head, with an attachment for Ponto Sound Processor, the softband comes in assorted colors, is adjustable for a snug and tailored fit.

5 IDENTIFICATION AND DESCRIPTION OF THE DEVICE

5.1 Device description

The Ponto Softband device is part of a skin-drive bone conduction, wherein a Ponto sound processor is attached to the band which allows for circumlocution of the function of the outer and middle ear. Acoustic sound pressure waves are picked up by the microphones in the externally mounted sound processor and this signal is converted to mechanical energy (vibrations) by the transducer in the sound processor. This signal is then transmitted through the skin to the temporal bone of the skull. The mechanical energy vibrates the temporal bones of the skull which are picked up by the hair cells within the cochlea in the inner ear where the mechanical energy is converted to electrical neural impulses and transmitted to the primary auditory cortex in brain via the auditory nerve.

The survey will focus on Softband 5 but will also allow for feedback from parents whose children previously or currently use any of the Softband generation models:

- Softband/Softband bilateral (initial CE 2010)

- Ponto Softband (initial CE 2016)
- Ponto Softband bilateral (initial CE 2017)
- Softband 5 (initial CE 2022)

Parents whose children have been fitted with a Ponto sound processor on a Ponto Softband will be surveyed.

The study will focus on devices from the following Ponto families:

- Ponto 3, Ponto 3 Power, Ponto 3 SuperPower
- Ponto 4
- Ponto 5 Mini, Ponto 5 SuperPower

5.2 Manufacturer

The Ponto sound processors as well as Oticon Medical Softbands are manufactured by Oticon Medical AB, Askim, Sweden. Oticon Medical AB is ISO 13485 certified and has CE-marked and FDA-cleared products for hearing healthcare.

5.3 Population and indications

The study population of interest is children below the age of 18 who are currently wearing a softband coupled to a Ponto sound processor. Parents or primary caregivers will be the surveyed population.

The softband solution is intended for children with conductive/mixed hearing loss and single-sided deafness who cannot be fitted or are waiting to be fitted with a surgically placed bone anchored hearing implant. It can often be recommended for individuals who do not benefit from conventional hearing aids who have ear problems such as blockages or infections, who present with a high likelihood of implant extrusions or skin care related burdens or who have thin or irregular skull bone (i.e. syndromic children).

6 JUSTIFICATION FOR THE INVESTIGATION

The study is a non-interventional, observational, study on users of Ponto sound processors who use their sound processors on a softband solution. The purpose of this study is to assess subjective benefit by evaluating performance and overall satisfaction of the Ponto on a Ponto Softband in pediatric users.

This study will utilize responses from survey questions of parents or primary caregivers of children fitted with a softband solution. The survey will collect responses relating to reported hearing improvements and quality of life.

The study will use the PEACH questionnaire¹ to evaluate performance. The PEACH is a measure used by hearing health professionals to evaluate the effectiveness of a child's use of hearing in real-world environments. PEACH is validated with norms scale (English). This study will also use the GCBI questionnaire², modified to specifically query a child's quality of life after receiving their Ponto sound processor on softband. Additionally, a specialized questionnaire is constructed to gather feedback on wear and general comfort of Oticon Medical Softband.

7 RISKS AND BENEFITS OF THE INVESTIGATIONAL DEVICE AND CLINICAL INVESTIGATION

Participants will be asked to complete a survey. No additional treatments or procedures will be utilized for this study. Therefore, only risks associated to data capture and data privacy have been identified and these

are mitigated by strict data management procedures (see Section 12).

Although participants included in this study might not receive any benefit from the study itself, the research project will promote a better understanding of satisfaction of the Ponto Softband solution which will be shared within the field of BAHS and may lead to improvements in future iterations of the oftband design.

Prior to enrollment into the study the participants will receive information about potential benefits and risks. Electronically signed consent based on this information will be required from all participants prior to collecting any study specific data.

8 OBJECTIVES AND HYPOTHESES

The purpose of the study is to evaluate subjectively reported hearing performance and overall satisfaction of Oticon Medical Ponto sound processors on softband.

8.1 Primary objective

Primary objective	Corresponding primary endpoint/outcome variable(s)	Section
A. To investigate hearing performance of children wearing Oticon Medical Ponto sound processors on Softband	PEACH questionnaire evaluating Aural/Oral performance of children in quiet, noise and overall.	9.2.1
B. To investigate overall satisfaction of Oticon Medical Ponto sound processors on Softband	GCBI questionnaire evaluating health related benefit after hearing intervention for children. By answering specialized questionnaire to gather feedback on wear and general comfort of the Oticon Medical Softband.	

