after a healthcare intervention. The GCBI is a parent-completed questionnaire comprised of 24 questions that query various aspects of a child's daily life and is worded to apply to children of any age. The GCBI is commonly modified to be used in any area of paediatric medicine. For this study, "operation" will be adapted to "Ponto sound processor on Softband", (Appendix B).

Softband specific questionnaire

The softband-specific questionnaire was developed by Oticon Medical and consists of questions designed to be completed by parents or other caregivers of children who are currently fitted with a Ponto sound processor on a softband.

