23 APPENDICES

A. PEACH

	Question	Never 0%	Seldom 1 - 25%	Sometimes 26 - 50%	Often 51 - 75%	Always 75-100%
1	How often has your child worn his/her hearing aids and/or cochlear implant?	0	1	2	3	4
2	How often has your child complained or been upset by loud sounds?	4	3	2	1	0
3	When you call, does your child respond to his/her name in a quiet situation?	0	1	2	3	4
4	When asked, does your child follow simple instructions or do a simple task in a quiet situation?	0	1	2	3	4
5	When you call does your child respond to his/her name in a noisy situation when he/she can't see your face? (examples of responses include looks up, turns, answers verbally)	0	1	2	3	4
6	When asked, does your child follow simple instructions or do a simple task in a noisy situation?	0	1	2	3	4
7	When you are in a quiet place reading with your child, how often does he/she pay close attention to what you are saying? OR if your child is listening to stories/songs on the TV or CD when there is no other background noise how often can he/she follow what is being said?	0	1	2	3	4
8	How often does your child initiate/participate in conversation in a quiet situation?	0	1	2	3	4
9	How often does your child initiate/participate in conversation in a noisy situation?	0	1	2	3	4
10.	How often does your child understand what you say in the car/bus/train?	0	1	2	3	4

11.	How often does your child recognize peoples' voices without seeing who was talking?	0	1	2	3	4
12.	How often does your child successfully use a phone?	0	1	2	3	4
13.	How often does your child respond to sounds other than voices?	0	1	2	3	4

B. GCBI questionnaire

1. Has your child's Ponto sound processor on softband made his/her overall life better or worse?						
a) much better b) a little better c) no change d) a little worse e) much worse						
2. Has your child's Ponto sound processor on softband affected the things he/she does?						
a) much better b) a little better c) no change d) a little worse e) much worse						
3. Has your child's Ponto sound processor on softband made his/her behaviour better or worse?						
a) much better b) a little better c) no change d) a little worse e) much worse						
4. Has your child's Ponto sound processor on softband affected his/her progress or development?						
a) much better b) a little better c) no change d) a little worse e) much worse						
5. Has your child's Ponto sound processor on softband affected how lively he/she is during the day?						

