a) much better b) a little better c) no change d) a little worse e) much worse						
6. Has your child's Ponto sound processor on softband affected how well he/she sleeps at night?						
a) much better b) a little better c) no change d) a little worse e) much worse						
7. Has your child's Ponto sound processor on softband affected his/her enjoyment of food?						
a) much better b) a little better c) no change d) a little worse e) much worse						
8. Has your child's Ponto sound processor on softband affected how self-conscious						

he/she is with other people?				
a) much better	b) a little better	c) no change	d) a little worse	e) much worse
9. Has your child's Ponto sound processor on softband affected how well he/she gets on with the rest of the family?				
a) much better	b) a little better	c) no change	d) a little worse	e) much worse
10. Has your child's Ponto sound processor on softband affected his/her ability to spend time and have fun with friends?				
a) much better	b) a little better	c) no change	d) a little worse	e) much worse
11. Has your child's Ponto sound processor on softband affected how embarrassed he/she is with other people?				
a) much better	b) a little better	c) no change	d) a little worse	e) much worse
12. Has your child's Ponto sound processor on softband affected how easily distracted he/she has been?				
a) much better	b) a little better	c) no change	d) a little worse	e) much worse
13. Has your child's Ponto sound processor on softband affected his/her learning?				
a) much better	b) a little better	c) no change	d) a little worse	e) much worse
14. Has your child's Ponto sound processor on softband affected the amount of time he/she has had to be off nursery, playgroup or school?				
a) much better	b) a little better	c) no change	d) a little worse	e) much worse
15. Has your child's Ponto sound processor on softband affected his/her ability to concentrate on a task?				
a) much better	b) a little better	c) no change	d) a little worse	e) much worse
16. Has your child's Ponto sound processor on softband affected how frustrated and irritable he/she is?				
a) much better	b) a little better	c) no change	d) a little worse	e) much worse
17. Has your child's Ponto sound processor on softband affected how he/she feels about him/herself?				
a) much better	b) a little better	c) no change	d) a little worse	e) much worse
18. Has your child's Ponto sound processor on softband affected how happy and content he/she is?				

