Ponto 5 SuperPower

I don't know / other model

10. Think about how much your child used their sound processor(s) over the past two weeks. On an average day, how many hours did they use the sound processor(s)?

none
less than 1 hour a day
1 to 4 hours a day
4 to 8 hours a day
more than 8 hours a day

**11. Think about a situation where your child wanted to hear better, before receiving their sound processor.
Over the past two weeks, how much has the sound processor(s) helped in that situation?**

helped not at all
helped slightly
helped moderately
helped quite a lot
helped very much

12. How satisfied overall are you with your child's Ponto experience?

very much
quite a lot
moderately
slightly
not at all

13. How satisfied overall are you with your child's softband?

very much
quite a lot
moderately
slightly
not at all

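### Softband comfort is listed within a primary outcome, but none of the 50 survey items asks about it

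*Combined protocol and SAP*

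**What the plan says.** Section 8.1, in the column that gives the primary endpoints and outcome variables, assigns two instruments to objective B (overall satisfaction): the GCBI and a "specialized questionnaire to gather feedback on wear and general comfort of the Oticon Medical Softband". Section 6 says the same of the instrument's purpose: "a specialized questionnaire is constructed to gather feedback on wear and general comfort of Oticon Medical Softband".

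Two other places describe this endpoint without mentioning comfort. The synopsis calls it "Outcomes of satisfaction questionnaire". Section 9.2.1 says only that the softband questionnaire "consists of questions designed to be completed by parents or other caregivers of children" fitted with the device, and lists no topics.

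The items themselves are printed in full in Appendix A (PEACH), Appendix B (GCBI) and Appendix C (softband questionnaire). Section 11 plans descriptive statistics only, with no imputation.

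**The concern.** An outcome named in Section 8.1 should be traceable to at least one item in the survey. Comfort is not. If the plan is followed exactly, the final report can describe satisfaction, benefit and hours of use, but it has no data on comfort.

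The practical hazard is that Appendix C item 13, overall satisfaction with the softband, ends up standing in for comfort because it is the only item that rates the band. It asks for no reason, so a high or low rating cannot be attributed to comfort rather than to sound quality, appearance, ease of use or anything else. Section 7 says the results may lead to improvements in later softband designs. A low rating on item 13 would not tell the sponsor what to improve.

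**Working it through.** **Step 1. Count the items.** Section 9.2.1 states 13 PEACH items and 24 GCBI items; Appendices A and B contain exactly those numbers. No count is stated for the softband questionnaire; Appendix C is numbered 1 to 13 without a gap.

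Total = 13 + 24 + 13 = 50.

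**Step 2. Check each item for comfort, fit, pressure, pain, skin effects of the band, or a free-text field.**

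| Instrument | Items | Nearest candidates | Comfort items |
|---|---|---|---|
| PEACH | 13 | Item 2: "How often has your child complained or been upset by loud sounds" (loudness tolerance) | 0 |
| GCBI | 24 | Items 6 (sleep), 8 (self-consciousness), 11: "affected how embarrassed he/she is with other people" (psychosocial effect) | 0 |
| Softband questionnaire | 13 | Item 13: overall satisfaction with the band | 0 |
| All | 50 | | 0 |

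The Appendix C items cover:
- current use, birth date and gender (1–3);
- duration of hearing problems and of device use (4–5);
- number of processors, softband model, first softband or not, and processor model (6–9);
- daily hours of processor use (10);
- how far the processor helped (11);
- satisfaction with the Ponto experience and with the softband (12–13).

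All are closed or factual items, and none invites a comment.

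**Step 3. Check what remains of objective B.** Overall satisfaction has two items (Appendix C 12 and 13), and benefit has the GCBI. Wear is measured indirectly: Appendix C item 10 asks about hours of sound-processor use, and PEACH item 1 asks about hearing aids or cochlear implants. Neither names the band, although the processor is worn on it.

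**Step 4. What one added item would deliver at the planned n = 40.** The plan gives no expected share or standard deviation, so these are assumed ranges, with all 40 participants answering.

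Wilson 95% interval: [p + z²/(2n) ± z·√(p(1−p)/n + z²/(4n²))] / (1 + z²/n), with z = 1.96.

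| Assumed share reporting discomfort | Count | 95% interval |
|---|---|---|
| 10% | 4/40 | 4.0% to 23.1% |
| 20% | 8/40 | 10.5% to 34.8% |
| 50% | 20/40 | 35.2% to 64.8% |

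If the item were scored 1 to 5, the half-width of the 95% interval for the mean is t(0.975, 39) × SD/√40:
- SD 0.8: 0.256
- SD 1.0: 0.320
- SD 1.2: 0.384

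These figures show what the remedy would buy. The size of the defect itself is simply 0 of 50 items.

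**The case against.** The strongest reply is that objective B is overall satisfaction, not comfort. The synopsis names a satisfaction questionnaire, items 12 and 13 answer it directly, and no hypothesis, sample size or analysis depends on comfort. On that reading the comfort phrase in Section 8.1 is a loose description of a questionnaire whose items are printed in the same document. This limits the importance of the point: objective B remains answerable. It does not remove the point, because the phrase stands in the endpoint column and is repeated in Section 6.

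It can also be said that nothing in the plan announces that item 13 will be reported as comfort. That is true; the misreading is a risk, not a stated intention.

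The precision figures rest on assumptions and describe a hypothetical item. A share reporting discomfort also needs a cut-off on the five-point scale. Both remarks are fair, and the finding does not depend on those figures.

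The wear component is also weaker than it looks, since no item names wear of the band. That stands as a qualification.

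Finally, Section 9.2.1 gives no item count for Appendix C, so unbroken numbering cannot by itself prove that item 13 is the last. But item 13 has its complete answer scale, and nothing suggests that further items existed.

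**Conclusion.** The concern holds. Sections 6 and 8.1 promise feedback on softband comfort, and 0 of the 50 items collect it (PEACH 0 of 13, GCBI 0 of 24, softband questionnaire 0 of 13). More participants cannot repair this. The gap is confined to the comfort component: satisfaction and benefit are measured directly, and wear is measured through hours of processor use. It should be fixed, but it does not threaten the whole of objective B. The conclusion rests only on the items as printed in Appendices A to C.

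**What to change.** Before data collection, add one closed item to Appendix C, for example *How comfortable is the softband for your child?*, with the five answer categories of item 13. Name it in Section 8.1 as the comfort outcome, and state that the number and percentage in each category will be reported. If a single share reporting discomfort is wanted, fix in advance which categories count. Use the same description of the questionnaire in the synopsis and in Sections 6, 8.1 and 9.2.1.

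The cost is one question on top of 50, plus an amendment to Appendix C and Section 8.1. Under Section 13, IRB/EC approval is needed if the change is substantial; if the study has been deemed exempt, notification is needed when the change might affect the exemption. Either takes some time. If the survey is already open, earlier respondents will lack the item, and because Section 11 allows no imputation, the result must be reported on those who were asked.

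If no item is added, delete the comfort wording from Sections 6 and 8.1, describe wear as hours of sound-processor use, and draw no conclusion on comfort. That costs only a wording change, but it gives up the comfort outcome.

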9 DESIGN OF THE CLINICAL INVESTIGATION

9.1 Subject population

The population for this study will be children who use a Ponto Sound Processors on a Ponto Softband in the United States. Parents or caregivers of users (hereforth referred for as “participants” who are part of Oticon Medical’s US user database, who signed up for inclusion in the database when fitted with a Ponto Sound Processor will be approached through email out-reach. When signing up for the database participants give their consent to be contacted by Oticon Medical. In all cases, study awareness and enrollment in this study will occur only after being fitted with Ponto sound processor(s) on a softband solution.

9.1.1 Inclusion criteria

The following participants will be included in the study:

	Title BC117 - Pediatric Performance and Satisfaction of Oticon Medical Ponto on Softband	Document no Doc-00121767	Revision 0	Page 8(17)
---	--	------------------------------------	----------------------	----------------------

- Individuals who are a parent or guardian of a softband user who are at or above the age of majority (AOM). AOM is 21 in Mississippi, 19 in Nebraska and Alabama, and 18 in all other US states.
- Participants provided study-specific consent before completing the survey.
- Users fitted with at least one Ponto Sound Processor on a softband at the time of the survey.

9.1.2 *Exclusion criteria*

The following participants will be excluded from the study:

- Participants who did not provide consent or later revoked consent.
- Under the AOM

9.1.3 *Number of Subjects*

The aim is to enroll 40 participants within 24 months.

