9.2 Investigation Procedures

Out-reach will be made through email to registered participants, parents or primary caregivers of children, fitted with a Ponto device on a softband in the US Salesforce database. The participants in the US Salesforce database had previously consented to being contacted by Oticon Medical in the future. The email will be sent through the Salesforce database and contain general information about the study as well as a link to the study landing page, created and hosted in SMART-TRIAL. On the landing page more information about the survey is provided and participants are asked to proceed with sign-up by providing their email address. At this point the participant is assigned a unique identification number. Following providing consent, the participant will be provided with access to the survey in SMART-TRIAL. Periodic reminders, one after one week, another after four weeks, and after five weeks will be sent from SMART-TRIAL if consent has been provided by survey not completed.

Out-reach efforts will also be made through Oticon Medical's social media accounts (such as linked-in, facebook, etc). Additionally, clinics and providers in the US who have active pediatric populations fitted with Ponto sound processors on softband who have expressed interest in assisting recruitment efforts may also be included in reach out efforts. Interested clinics will be provided with a one-page informational flyer to provide to parents of children who meet the inclusion criteria. The flyer will have the same information as the social media postings as well as emails sent to the users in the Salesforce database.

9.2.1 *Surveys*

PEACH

The Parent's Evaluation of Aural/Oral Performance of Children (PEACH) was developed to evaluate the effectiveness of amplification for infants and children with hearing impairment by a systematic use of parents' observations. The PEACH questionnaire is composed of 13 questions that examines a child's auditory performance in quiet and noisy listening conditions and has been shown to have good internal consistency and high test-retest reliability. The PEACH can be used with infants as young as one month old and with school-aged children who have hearing loss ranging from mild to profound degree.

GCBI

The Glasgow Children's Benefit Inventory (GCBI) was designed to retrospectively assess quality of life benefits

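### Does the plan leave open which survey responses enter the summaries and count toward the 40?

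*Combined protocol and SAP*

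**What the plan says.** **Population.** The synopsis admits a parent or primary caregiver of a child under 18 who is "currently using a Ponto Softband for Ponto Sound Processor". Section 5.3 gives the population of interest as "children below the age of 18 who are currently wearing a softband coupled to a Ponto sound processor". Section 9.1.1 opens with "Individuals who are a parent or guardian of a softband user who are at or above the age of majority (AOM"), an age condition on the adult respondent. Its third bullet requires that the user have at least one Ponto processor fitted on a softband when the survey is taken. Neither 9.1.1 nor 9.1.2 repeats the child's age limit. Section 5.1 says the survey will also allow "feedback from parents whose children previously or currently use any of the Softband generation models".

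**Route into the survey.** Under section 9.2 a person signs up on the landing page with an email address, and "At this point the participant is assigned a unique identification number". Then: "Following providing consent, the participant will be provided with access to the survey in SMART-TRIAL". Current use and date of birth are items 1 and 2 of Appendix C, inside the survey. The text prints no consequence for answering No to item 1 or for an age of 18 or over.

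**Target and analysis.** The synopsis sets the duration as "24 months or when targeted number of participants (40) have been enrolled". Section 9.1.3 says "The aim is to enroll 40 participants within 24 months". Section 11 plans means, standard deviations, medians and ranges without imputation, says the sample size does not come from a hypothesis, and names no analysis set. Section 14 leaves the effect of protocol deviations on the analysis to the end of the study.

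**The concern.** Descriptive summaries are the whole output of this study, so the group being described is the main thing an analysis section has to define. Section 11 does not define it. The operative criteria omit the child's age, eligibility is recorded only after survey access is given, and the one sentence linking departures from protocol to the analysis defers the matter until the data are in. That looks like room to choose responses after seeing them.

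The plan's own text makes stray entries foreseeable. Families join the database when the child is fitted, which may be years before the survey. Section 5.3 says some children are waiting for an implant and so may since have stopped using a softband. Social media recruitment reaches anyone. Section 9.2 plans three reminders for people who consented but did not finish, so non-completion is expected.

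If such entries counted as enrolled, recruitment could close with fewer than 40 usable responses, and the denominators of the PEACH, GCBI and satisfaction summaries would be unclear.

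**Working it through.** **1. Can the 40 be reproduced?** No. Section 11 attributes it to the number of eligible database users and to earlier response rates, and gives neither. There is no power, effect size, standard deviation or precision target that a shortfall would miss.

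**2. Is any type of response left without a rule?**

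| Response | Text that decides it | Result |
|---|---|---|
| Child 18 or over (item 2) | Synopsis criteria; 5.3 | Outside the study |
| Child not currently using (item 1 = No) | Synopsis criteria; 5.3; third bullet of 9.1.1 | Outside the study |
| Respondent under the age of majority | 9.1.1; 9.1.2 | Outside the study |
| Email sign-up without consent | 9.1.1; 9.1.2; section 7 (consent before any study data) | Outside the study |
| Consent later withdrawn | 9.1.2 | Outside the study |
| Eligible, consented, survey partly completed | Section 11: no imputation | Items answered can be summarised |
| Eligible, consented, nothing completed | No text | Nothing to summarise; unclear only whether counted in the 40 |

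Only the last row is open, and it affects the recruitment count, not the content of a summary. The identification number given at sign-up does not define enrolment, because a person without consent is excluded. The subject number in section 12 concerns coding and privacy.

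**3. Does section 5.1 admit former users?** Its sentence lists softband generations. Item 8 of Appendix C asks whether this is the child's first softband, and one answer is that a different generation was used before. The natural reading is a current user who once had an older model, which does not conflict with 5.3.

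**4. How much precision could be lost?** The plan reports no standard errors or intervals, so this is only a gauge. All loss rates here are assumptions.

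Loss of k from 40, with the standard deviation unchanged: ratio of standard errors = √(40/(40 − k)).
- k = 1: √(40/39) = 1.013
- k = 2: √(40/38) = 1.026
- k = 4: √(40/36) = 1.054

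For larger losses, such as many non-completers, take a share d lost. The usable number is n = 40(1 − d), the 95% half-width for a mean in standard deviation units is t(0.975, n − 1)/√n, and the enrolment needed for 40 usable is 40/(1 − d), rounded up.

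| d | n usable | Half-width (SD) | Enrolled for 40 usable |
|---|---|---|---|
| 0% | 40 | 0.32 | 40 |
| 10% | 36 | 0.34 | 45 |
| 20% | 32 | 0.36 | 50 |
| 30% | 28 | 0.39 | 58 |
| 40% | 24 | 0.42 | 67 |

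Even with 40% lost, the half-width grows by 0.10 SD. Counting usable responses in place of enrolled people would mean recruiting more within the same 24 months; it would not alter what is estimated.

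**The case for a change.** The strongest case is that eligibility criteria and an analysis set are different things. The criteria say who should be in the study. They do not say what happens to data already collected from someone who proves ineligible, and section 14 could be read as leaving that to judgement at the end. In a study with nothing but summaries to report, one sentence in section 11 would remove the doubt at almost no cost, since items 1 and 2 are already asked.

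Part of this stands. Section 9.1.1 should have carried the child's age limit, section 11 could have named the responses it summarises, and enrolled could have been defined.

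The claim that nothing set in advance decides which responses count does not stand. Section 9.1.1 and the synopsis state who is included, and leaving out a response that fails those criteria applies the plan as written. Section 14 deals with deviations and does not replace the criteria. Targeting before the survey also limits the number of ineligible entries: emails go to registered caregivers of children fitted on a softband, and flyers are for parents whose children meet the criteria. Social media is the open channel. The landing-page text is not reproduced and consent pages were removed from the copy reviewed, so it cannot be said that no eligibility wording appears before the survey.

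**Conclusion.** The gaps in wording are real, but no change is needed. The child's age limit and current use are fixed in the synopsis and 5.3, the third bullet of 9.1.1 supports current use, and the survey records both facts. An analyst following the documents would set aside responses that fail those criteria, summarise the available answers from the rest, and give the number behind each questionnaire.

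The one point left open is whether consented non-completers count toward the 40. It bears on a recruitment aim with no power or precision target behind it. Losing 1, 2 or 4 of 40 would widen a standard error by 1.3%, 2.6% or 5.4%, and the assumed range up to 40% lost moves a 95% half-width from 0.32 to 0.42 SD. No stated figure would be wrong, and there is no test or decision rule to disturb.

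This rests on two assumptions: that the synopsis criteria are applied together with those in 9.1.1, and that section 5.1 refers to earlier softband generations of current users. If the sponsor meant former users to be analysed, the criteria and 5.1 would conflict, but nothing else in the documents points that way.
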